5.3 Inclusion Criteria

1. A male or female patient who has had prior ESS and who is indicated for office endoscopy by the ENT specialist
2. Patient age: adult (>18 years old)
3. A patient who is able to understand the requirements of the study, is willing to comply with its instructions and schedules, and agrees to sign the informed consent

5.4 Exclusion Criteria

1. Any medical disorder which in the investigator's judgment contraindicates the patient's participation
2. Pregnancy

6 INVESTIGATION PLAN

6.1 Study Design

Type of Study

This is an open, single-center, prospective study in which the investigational device, the Peregrine Drivable ENT Scope, will be tested in a single group of adult patients, male or females.

The rationale behind this study is to show that the ability to visualize intra-sinus anatomic landmarks of the Maxillary, Frontal and Sphenoid sinuses is comparable to or better than the ability to visualize them with a Standard 70° 4mm Endoscope in the office setting; This study will evaluate the safety and performance of the Peregrine endoscope which enables intra-sinus visualization as a first step to assess potential benefits, such as minimizing CT scans and associated radiation exposure, change in medication regimen, referral to revision surgery, saving multiple office visits, and cost.

This study is proposed after completing a series of clinical cases with the Sinusway endoscopy system, (which is similar to the Peregrine Endoscopy system) which demonstrated that the system is safe and performed well to physician's satisfaction (detailed information on the studies is provided in the Investigator's Brochure).

Measures to Minimize Bias

Subjects shall constitute their own control group by comparing the ability to visualize intra-sinus anatomic landmarks and pain and tolerability between Peregrine and a standard endoscope in the same subject. For this reason, no randomization is necessary in this study.

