4.3 Study End Points

Primary - Safety

All adverse device effects will be captured and summarized as defined in **Section-8**. Adverse device effects (type, frequency, severity) are expected to be similar to those reported in the literature for Nasal Endoscopy (section 8).

For this study, the Safety comparison with the data of Nasal Endoscopy reported in the literature will be descriptive with no statistical endpoints.

Primary – Performance

Evaluation of ability of Peregrine and the comparison endoscope to access and visualize sinus anatomy at the following landmarks:

- Maxillary (ostium, anterior wall, lateral aspect, floor)
- Frontal (ostium, posterior wall, anterior wall, lateral recess)
- Sphenoid (ostium, sella, floor, lateral recess)

Subjects will be evaluated with:

- a. Mandatory – Peregrine Endoscope (the study device)
- b. Mandatory – A Standard 30° 4mm endoscope
- c. Optional – A Standard 70° 4mm endoscope
- d. Optional – A standard Flexible Endoscope

- Visualization success rates, calculated as the No. of successes divided by the No. of attempts, will be confirmed by direct visualization.
- Representative images of the accessed anatomic landmarks will be recorded.
- Level of prior resection will be recorded – anterior or posterior ethmoidectomy, draf IIa, draf IIb, uncinatectomy, antrostomy, maxillectomy, sphenoidotomy, dilation

Secondary - Performance

- Image quality – will be assessed through a yes/no statement regarding adequacy of Peregrine image quality for office endoscopy procedures, in comparison to the comparison device.
- Patient pain and tolerability will be assessed through validated VAS for both Peregrine and the comparison endoscope.
- Impact of Peregrine's extended visualization capability on clinical workflow will be evaluated through a series of questions regarding identification of pathology, evaluation of mucosa, change in medical management, need for additional CT scan, indication for revision surgery, etc.
- Peregrine ease-of-use will be evaluated through a user questionnaire.

Other Measurement – Performance and effectiveness

- Irrigation (through Peregrine working channel) will be documented (performed/not performed), when performed.
- To evaluate nasal cavity inflammation and sinuses inflammation using Lund Mackay CT score and Lund Kennedy Endoscopic scoring, if applicable.

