6.2 Study Procedures

Visits 1: Screening and Enrollment

- Screening will take place at the day of procedure or within 1 day-30 days before the procedure as part of a regular office visit.
- Patients who potentially qualify for the study will be offered an Informed Consent to sign prior to further evaluation. Any patients who do not qualify will be exited from the study as screening failures and will not be included in the safety/effectiveness analyses.
- The following assessments will be performed before the procedure for each patient:
 - Medical history (including concomitant medications deemed relevant by the investigator)
 - Sino-Nasal outcome test (SNOT-22)
 - Vital signs – optional
 - CT scan – optional - as available in the patient file.
 - Nasal Cavity and sinuses inflammation score will be captured using the Lund Mackay CT
 - Compliance with inclusion/exclusion criteria
 - Patients found eligible to participate in the study during visit 1 will be scheduled to undergo nasal endoscopy evaluation with Peregrine.

Visit 2: Procedure

The procedure will be office endoscopy as part of a routine post-operative office visit or due to recurrence of symptoms. Visits 1 and 2 can be combined into a single visit.

- **Before the procedure:**
 - Eligible subject/s will attend the Medical Center at the day of procedure and will be inquired by the PI regarding changes to their health status since the screening visit. If at this point it is

determined that the patient **does not** meet all Inclusion and Exclusion criteria and cannot be treated, the patient will be exited from the study. These patients will be considered screening failures and will not be included in any of the safety or efficacy endpoint analyses.

- **Endoscopy:**

1. Patients will undergo the procedure under local or topical anesthesia, at physician discretion.
2. The Peregrine endoscopy system will be prepared for use per its instructions for use.
3. Obligatory – the surgeon will attempt to visualize the pre-defined sinus anatomy landmarks with a standard 30° 4mm endoscope which will be recorded as success/failure, and an image of the anatomic landmarks visualized will be taken. Patient will be asked to score the endoscope for pain and tolerability.

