4. Obligatory – the surgeon will then attempt to visualize the pre-defined sinus anatomy landmarks with Peregrine endoscope which will be recorded as success/failure, and an image of the anatomic landmarks visualized will be taken. Patient will be asked to score Peregrine for pain and tolerability.
5. Optional – the surgeon will have the option to attempt to visualize the pre-defined sinus anatomy landmarks with a standard 70° 4mm endoscope and/or a flexible endoscope which will be recorded as success/failure, and an image of the anatomic landmarks visualized will be taken. Patient will be asked to score the endoscope for pain and tolerability.
6. Optional - irrigation of the nasal anatomy will be performed and recorded as Done/Not Done and which sinus was irrigated.
7. The physician will answer a set of questions related to endoscope usability and utility in clinical decision making in comparison to the standard endoscope.
8. The procedure will be recorded by site's AIDA system to enable the physician to perform assessments post procedure.

- **After the procedure:**

- The patient will recover from the procedure according to center's common practice. Before the patient is dismissed, recording of AE, if any, will be performed. Patient will exit the study.

Visit 3: Telephone Follow-up visit

- Telephone Follow-up for safety assessment will be conducted by study personnel two weeks \pm 3 days following patient last study visit.
- In the absence of any on-going ADE's, the patient will exit the study and Exit Form will be completed.

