6.3 Methods and Timing for assessments

Schedules of assessments are listed in **Table No. 1 below**.

Table 1: Study visit schedule

Study Activities	Visit I: Screening and Inclusion	Visit II: Procedure At day of screening or within 30 days post screening	Visit III: Telephone Follow-up Up to 2 weeks ± 3 days from visit II
Informed Consent	X		
Demographic Data	X		
Medical History	X		
SNOT 22	X		
Concomitant medication related to sinus disease	X		
Physical Examination	X		
Vital Signs (optional)	X		
Inclusion/exclusion criteria	X		
CT scan (as available)	X (optional)		
Lund Mackay/Kennedy inflammation score	X		
Endoscopy with Peregrine and a standard Endoscope		X	
User questionnaire		X	
Patient tolerability and pain score		X	
AEs/SAEs		X	X
Patient Exit			X

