7 STATISTICAL CONSIDERATIONS AND SAMPLE SIZE

Statistical Considerations

Demographic and baseline characteristics will be summarized for all subjects included in the analysis. Continuous variables will be summarized using summary statistics (mean, standard deviation, median, range combined with 95% confidence interval calculations) and categorical variables will be summarized using counts and percentages.

In particular, the following tests according to the parameters type are going to be performed:

- Continuous parameters will be presented by the estimated value and calculation of 95% confidence intervals. In addition, the comparison will be by using the relevant Student's t-test.
- Categorical parameters will be analyzed by Fisher exact test/ chi-square tests (in case of low observed frequencies).

Tests will be two-sided in accordance to the hypothesis regarding the tested parameters, with a significance level of 0.05.

Sample Size

Up to thirty (30) patients are expected to complete the study.

The primary endpoint of the study will be to demonstrate that the Peregrine Endoscope will perform comparable to or better than a Standard 70° 4mm Endoscope, where a difference of 20% or more between visualization success rates will be considered to be statistically significant. Per protocol, a subgroup analysis of each of the different sinus cavities (i.e., Frontal, Maxillary and Sphenoid) will be used for power calculation.

In order to maintain minimal Power 80% and Type I ($=\alpha$) error of 5% to detect minimal differences of $\pm 20\%$, a sample size of 7 samples is needed per sinus cavity. This number does not include an estimated 20-30% drop-out rate due to technical reasons unrelated to the device. Therefore, a sample size of 10 samples per each sinus cavity, and a total of 30 samples for all sinuses (total of up to 30 patients), will be recruited to the study.

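### Own-control does not remove order effects: the 30° scope always goes first and Peregrine second, so any order effect is confounded with device

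*Combined protocol and SAP*

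**What the plan says.** Section 6.1 describes an open, single-group study. Under the heading on minimizing bias it makes each subject their own control for visualization and for pain and tolerability, and concludes: "For this reason, no randomization is necessary in this study".

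Section 6.2 fixes one sequence for all patients:
- Step 3 (obligatory): "the surgeon will attempt to visualize the pre-defined sinus anatomy landmarks with a standard 30° 4mm endoscope". Success or failure is recorded and the patient scores pain and tolerability.
- Step 4 (obligatory): "the surgeon will then attempt to visualize the pre-defined sinus anatomy landmarks with Peregrine endoscope". The same items are recorded.
- Step 5 (optional): a 70° and/or a flexible scope.
- Step 7: the physician answers questions on usability and "utility in clinical decision making in comparison to the standard endoscope".
- Step 8: the procedure is recorded for later assessment by the physician.

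Section 7 lists t-tests and Fisher or chi-square tests, with no order or period term. Its sample size text sets a threshold: "where a difference of 20% or more between visualization success rates will be considered to be statistically significant". The documents provide no alternation of order, no washout and no independent reader.

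**The concern.** A within-patient comparison removes whatever differs between patients. It does not remove the effect of being the first or the second scope in the same nose within one session. Here position and device are the same variable: Peregrine is always second to the 30° scope.

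The effect could act in either direction. A surgeon who has just searched for a landmark may find it more easily on the second look. Irritation or bleeding from the first pass, or fading anesthesia, could make the second look harder or more painful.

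The primary visualization comparison and the secondary pain comparison are both exposed. Each would report device plus order as one number. With the sign unknown, the result can be neither corrected nor safely read as conservative.

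**Working it through.** The plan gives no figure for an order effect, so there is none to reproduce. The stated sample size does not enter this point. The only figure used from the plan is the 20-point threshold.

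**1. What the fixed order estimates.** Let D be the device difference (Peregrine minus 30°) and E the effect of being second rather than first.
- 30° first, Peregrine second: expected paired difference = D + E.
- Peregrine first, 30° second: expected paired difference = D - E.

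The plan has only the first kind of patient. That gives one equation with two unknowns, so no analysis can recover D. With both orders, and the same E for both scopes, the average of the two within-order means is [(D + E) + (D - E)]/2 = D.

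**2. Illustration of size (all inputs assumed).** Take equally good scopes, with p = first-pass success (50-80%), r = share of misses recovered on the second look (0-50%) and l = share of successes lost on the second pass (0-25%). The apparent difference is (1 - p)r - p·l.

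| p | gain only, r = 0.5 | loss only, l = 0.25 |
|---|---|---|
| 0.5 | +25 points | -12.5 points |
| 0.6 | +20 | -15 |
| 0.7 | +15 | -17.5 |
| 0.8 | +10 | -20 |

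The range is -20 to +25 points with no true device difference. It is 0 if neither effect exists or if they cancel. No figure is offered for pain.

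**3. Simulation.** 100,000 runs of 10 pairs, no device difference, first-scope success 0.60, independent results (all assumed).

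| E (points) | mean difference, fixed order | mean difference, order split 5:5 | chance of +20 or more, fixed | chance of +20 or more, 5:5 |
|---|---|---|---|---|
| -20 | -20 | about 0 | 6% | 25% |
| 0 | about 0 | about 0 | 25% | 25% |
| +10 | +10 | about 0 | 41% | 24% |
| +20 | +20 | about 0 | 60% | 23% |

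Under the fixed order the whole order effect appears as a device difference. Balancing removes that bias. It does not remove the sampling noise of 10 pairs, hence the 25% at E = 0.

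**4. What the randomized average estimates if the scopes differ.** In the step 2 model the order effect depends on each scope's own success rate. Let D be the first-pass difference pP - p30. The average of the within-order means is then D × [1 - (r + l)/2].

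| p30 | pP | r | l | D | fixed order | randomized average |
|---|---|---|---|---|---|---|
| 0.6 | 0.8 | 0.5 | 0 | +20 | 20 + 10 = +30 | 20 × 0.75 = +15 |
| 0.5 | 0.7 | 0.5 | 0.25 | +20 | 20 - 2.5 = +17.5 | 20 × 0.625 = +12.5 |
| 0.5 | 0.8 | 0.5 | 0.25 | +30 | 30 - 10 = +20 | 30 × 0.625 = +18.75 |

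The average is exact when D = 0 or when E is the same for both scopes. Otherwise, under this model, it is pulled toward zero. In the last two rows the fixed order happens to lie nearer to D, because gain and loss partly cancel.

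**5. Chance imbalance within a cavity.** If one cavity's 10 patients come from a 30-patient list split 15:15, the chance of a 7:3 or worse split is 24.5%. At 7:3 an unadjusted mean keeps (7 - 3)/10 = 40% of the order effect. Averaging the within-order means removes it, at a standard error larger by √(1/7 + 1/3)/2 ÷ √(1/10) = 1.09, or about 9%.

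**The case against.** - *The sentence is about arms.* In a single-group study there is nothing to allocate, and on that reading no randomization is indeed needed. But the sentence stands under the heading on minimizing bias and refers to the within-subject comparison itself, where the open question is order.
- *The surgeon may already know the anatomy.* A CT may be on file, and Table 1 lists "Lund Mackay/Kennedy inflammation score" at Visit I. But the CT is optional and Section 4.3 has "Lund Kennedy Endoscopic scoring, if applicable". Prior knowledge could reduce a second-look gain. It would not remove the confounding, and it does not bear on pain. The step 8 recordings only document what happened in the fixed order.
- *Standard scope first serves the workflow question.* This stands. Step 7 asks for a comparison with the standard scope, and an impression formed before Peregrine is used has value. It is a reason to allow the fixed order with a stated limitation.
- *The numerical range rests on chosen inputs.* This also stands. -20 and +25 are corners of assumed ranges, and the documents support neither as a likely value.
- *Randomizing is not exact in general.* Correct, as step 4 shows; the plan should say what the average estimates.

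A reader might infer that the fixed order favors Peregrine. The documents do not support that, because they give no sign.

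**Conclusion.** The point holds. For the 30°-versus-Peregrine pair, order is fully confounded with device in the primary visualization comparison and in the pain comparison, and own-control does not address this. That follows from the text alone and needs no assumed number.

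The size and sign of any order effect are unknown. The -20 to +25 points are an illustration under assumed inputs. They show only that an order effect could be as large as the plan's own 20-point threshold, not that it is.

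Two stronger readings go too far. One is that the differences must not be reported at all: Section 6.1 presents the study as a first step, and a clearly stated limitation is proportionate. The other is that randomizing always returns the first-pass device difference: it does so only with no device difference or with the same order effect for both scopes.

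**What to change.** **Preferred: randomize the order.**
- Assign the order of Peregrine and the mandatory 30° scope 1:1 per patient from a concealed list prepared in advance. Use one order for all of a patient's cavities, with any optional scopes after both. Record the order on the CRF.
- In Section 7, estimate the device difference as the average of the two within-order mean paired differences, and also report each within-order difference. State that this average is free of order bias when there is no device difference or when the order effect is the same for both scopes. Otherwise it estimates the device difference averaged over first and second position, which can differ from the first-pass difference.
- In Section 6.1, replace the sentence with: *Each subject is their own control; the order of the two mandatory endoscopes is assigned at random.*

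Cost: a short amendment, one list and one CRF field, with no added patients or procedures. Downsides: in about half of the patients (about 15 of up to 30) the step 7 answers lose a standard-only first impression, so they are best reported by order. Open scoring by the same surgeon also remains.

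**Alternative, if the workflow question has priority.** Keep the fixed order and correct the Section 6.1 sentence. State in Sections 6.1 and 7 that the visualization and pain differences combine device and order and must be interpreted with that limitation. This costs text only.

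**Cross-reference.** The Synopsis (methods and sample size) and Section 6.2 name the 30° scope as the comparator or mandatory scope. Section 6.1 names the 70° scope, and Section 7 has "the Peregrine Endoscope will perform comparable to or better than a Standard 70° 4mm Endoscope". This is a separate issue, and those passages must be reconciled. The figures above apply to the 30° pair only.

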6.2 Study Procedures

Visits 1: Screening and Enrollment

- Screening will take place at the day of procedure or within 1 day-30 days before the procedure as part of a regular office visit.
- Patients who potentially qualify for the study will be offered an Informed Consent to sign prior to further evaluation. Any patients who do not qualify will be exited from the study as screening failures and will not be included in the safety/effectiveness analyses.
- The following assessments will be performed before the procedure for each patient:
 - Medical history (including concomitant medications deemed relevant by the investigator)
 - Sino-Nasal outcome test (SNOT-22)
 - Vital signs – optional
 - CT scan – optional - as available in the patient file.
 - Nasal Cavity and sinuses inflammation score will be captured using the Lund Mackay CT
 - Compliance with inclusion/exclusion criteria
 - Patients found eligible to participate in the study during visit 1 will be scheduled to undergo nasal endoscopy evaluation with Peregrine.

Visit 2: Procedure

The procedure will be office endoscopy as part of a routine post-operative office visit or due to recurrence of symptoms. Visits 1 and 2 can be combined into a single visit.

- **Before the procedure:**
 - Eligible subject/s will attend the Medical Center at the day of procedure and will be inquired by the PI regarding changes to their health status since the screening visit. If at this point it is

determined that the patient **does not** meet all Inclusion and Exclusion criteria and cannot be treated, the patient will be exited from the study. These patients will be considered screening failures and will not be included in any of the safety or efficacy endpoint analyses.

- **Endoscopy:**

1. Patients will undergo the procedure under local or topical anesthesia, at physician discretion.
2. The Peregrine endoscopy system will be prepared for use per its instructions for use.
3. Obligatory – the surgeon will attempt to visualize the pre-defined sinus anatomy landmarks with a standard 30° 4mm endoscope which will be recorded as success/failure, and an image of the anatomic landmarks visualized will be taken. Patient will be asked to score the endoscope for pain and tolerability.
4. Obligatory – the surgeon will then attempt to visualize the pre-defined sinus anatomy landmarks with Peregrine endoscope which will be recorded as success/failure, and an image of the anatomic landmarks visualized will be taken. Patient will be asked to score Peregrine for pain and tolerability.
5. Optional – the surgeon will have the option to attempt to visualize the pre-defined sinus anatomy landmarks with a standard 70° 4mm endoscope and/or a flexible endoscope which will be recorded as success/failure, and an image of the anatomic landmarks visualized will be taken. Patient will be asked to score the endoscope for pain and tolerability.
6. Optional - irrigation of the nasal anatomy will be performed and recorded as Done/Not Done and which sinus was irrigated.
7. The physician will answer a set of questions related to endoscope usability and utility in clinical decision making in comparison to the standard endoscope.
8. The procedure will be recorded by site's AIDA system to enable the physician to perform assessments post procedure.

- **After the procedure:**

- The patient will recover from the procedure according to center's common practice. Before the patient is dismissed, recording of AE, if any, will be performed. Patient will exit the study.

Visit 3: Telephone Follow-up visit

- Telephone Follow-up for safety assessment will be conducted by study personnel two weeks \pm 3 days following patient last study visit.
- In the absence of any on-going ADE's, the patient will exit the study and Exit Form will be completed.

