2 SYNOPSIS

Protocol Number	PG-001
Protocol Title	Safety and Effectiveness Evaluation of the Peregrine™ Drivable ENT Scope for Office Endoscopy of the Paranasal Sinuses in Patients who underwent ESS
Participating Centers	Emory University, Atlanta, GA
Clinical Phase	Open, single-center, prospective
Investigational Study Device	Peregrine™ Drivable ENT Scope, by 3NT Medical
Study Procedures	
Up to 30 Patients, out of which are at least 10 samples per each of the frontal, maxillary and sphenoid sinuses, who have had prior ESS and are scheduled for nasal endoscopy in the office as part of a routine post-operative office visit or due to recurrence of symptoms, will be evaluated with Peregrine Endoscope. The patients will attend the following visits:
 
 1. Visit 1: Screening and Enrollment – as part of a regular office visit 2. Visit 2: Sinonasal endoscopy – evaluation with Peregrine and standard endoscopes 
Visits 1 and 2 can be combined into a single visit.

Study Population	Patients who have had prior ESS
Study Purpose	To assess the safety and effectiveness of Peregrine endoscope in patients in the office setting in terms of access into and visualization of the paranasal sinus anatomy, image quality, patient tolerability and clinical utility.
Study Endpoints	
Primary – Performance and Safety Endpoints:
 
 • To compare visualization success rates of the paranasal sinus anatomy by Peregrine and by a standard endoscope used in the office setting. • Device related adverse events 
Secondary – Performance Endpoints:
 
 • To assess the adequacy of the image quality of Peregrine for endoscopy procedures in the office. • To evaluate patient tolerability and pain • To evaluate the impact of extended visualization by Peregrine on clinical workflow

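### The clinical-workflow endpoint has no management plan recorded before Peregrine, and its questions are listed after the optional scopes, so a reported change cannot be reliably verified

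*Combined protocol and SAP*

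**What the plan says.** The Synopsis lists among the secondary performance endpoints "To evaluate the impact of extended visualization by Peregrine on clinical workflow". Section 4.3 says this will be assessed through "a series of questions regarding identification of pathology, evaluation of mucosa, change in medical management, need for additional CT scan, indication for revision surgery", among other items.

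Section 6.2 (Visit 2, Endoscopy) gives a numbered procedure:
- Step 3 is the mandatory "standard 30° 4mm endoscope which will be recorded as success/failure, and an image of the anatomic landmarks visualized will be taken". The patient also scores pain and tolerability.
- In step 4, "the surgeon will then attempt to visualize the pre-defined sinus anatomy landmarks with Peregrine endoscope", with the same items recorded.
- In step 5, "the surgeon will have the option to attempt to visualize the pre-defined sinus anatomy landmarks with a standard 70° 4mm endoscope" and/or a flexible scope, again with the same items recorded.
- Step 6 is optional irrigation.
- Step 7 is the only place where utility is assessed: "The physician will answer a set of questions related to endoscope usability and utility in clinical decision making in comparison to the standard endoscope".
- Step 8 provides for a recording of the procedure, so that the physician can make assessments later.

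Table 1 in Section 6.3 has one questionnaire row, marked once, at Visit II.

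**The concern.** A change in management is a difference between two states: what the physician would have done on the 30° view alone, and what the physician would do after also seeing the Peregrine view. The protocol text captures neither state at the time it exists. It captures one answer, listed after every scope has been used.

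Two separate weaknesses follow. The first applies to every patient: with no plan recorded before Peregrine, the starting point is reconstructed by a physician who knows which device is under study and what it showed. The second applies only where a 70° or flexible scope is also used: if the questions are answered in the listed order, that scope's findings are already known. Its use is at the surgeon's option with no stated criterion, so the affected patients are self-selected.

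Section 6.1 presents the study as a first step towards showing benefits such as fewer CT scans, altered medication and referral for revision surgery. These questions are the study's direct evidence on those benefits, so their credibility matters even though the endpoint is secondary.

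**Working it through.** The plan states no figure for this endpoint, so there is nothing to reproduce. The check is a trace of what is recorded, and when.

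**1. Is intended management recorded before Peregrine?**
- Visit 1 (Section 6.2): history, relevant medication, SNOT-22, optional vital signs, CT if available, an inflammation score and eligibility. No management plan.
- Table 1: adds demographics, physical examination and the Lund Mackay/Kennedy score. The score measures inflammation, not intended management. There is no row for a plan.
- Step 3: landmark success or failure, an image, and a pain and tolerability score. No plan.
- Count of plans recorded before Peregrine: 0.

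**2. Is utility assessed between Peregrine and the optional scopes?**
- Step 4 records the same three items as step 3. Step 5 then allows examination "with a standard 70° 4mm endoscope and/or a flexible endoscope".
- Count of utility assessments between steps 4 and 5: 0.
- Count of utility assessments in the whole procedure: 1 (step 7), listed after all scopes.

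**3. Does another part of the plan cover the gap?**
- The own-control argument in Section 6.1 covers visualization, pain and tolerability. It does not mention decision making.
- Section 7 gives general methods for continuous and categorical data and nothing specific to this endpoint.
- The step 8 recording is for the physician's own later assessments. It preserves what was seen, but cannot recover a plan that was never written down.

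**4. Is the reference scope clear?**
- The sample size text in the Synopsis names the 30° scope as comparator. Sections 6.1 and 7 name the 70° scope.
- Steps 3 and 5 describe both as standard, and step 7 refers to the standard endoscope without an angle. A physician who has used both is not told which one to compare with.

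**5. How large could the optional-scope effect be?**
The number of patients whose change is wrongly credited to Peregrine is

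N × (share given an optional scope) × (share of those whose management changed because of it) × (share of those changes credited to Peregrine).

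N is up to 30. The documents give none of the three shares. If any share is 0, the result is 0. If all are 1, it is 30 × 1 × 1 × 1 = 30. That is the logical range, not an estimate.

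**The case against.** The strongest case on the other side has five parts.

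- **The questions are comparative.** Step 7 asks for a comparison with the standard endoscope, and Section 4.3 ties the questions to Peregrine's extended view. A reader might infer from the sequence that changes cannot be attributed to Peregrine at all. The documents do not support that: the physician does give an attribution. It is subjective, unblinded and uncheckable, but it exists.
- **The timing is inferred.** Step 7 carries no timing word, whereas step 4 says that it follows step 3. Step 8, the recording, must run during the procedure, so the list is not strictly chronological. A reader might infer that the questions must be answered after the optional scopes. The text allows that but does not require it. It does not require earlier completion either, so practice may differ between patients.
- **The questionnaire is unseen.** Neither it nor the CRF is in the documents. Its items could ask about each scope separately, or about the plan held before Peregrine. A question put at the end would still be answered from memory.
- **There are partial safeguards.** Landmark results and images are recorded within each scope's own step, so one can check which scope reached which landmark. This limits how freely a later scope's findings could be credited to Peregrine, but it does not show what the physician intended to do.
- **The endpoint is modest.** It is secondary, with no stated hypothesis, threshold or power, in an open single-center study of up to 30 patients. A physician-reported questionnaire is a legitimate descriptive choice in that setting.

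The first four set the limits of the claim. The fifth sets its priority. None of them supplies the missing baseline.

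**Conclusion.** The point holds in limited form. On the protocol text, a reported change in management is a retrospective judgement by an unblinded physician and cannot be reliably verified. This applies to all patients, whether or not an optional scope is used. In those who receive one, the answer may partly reflect that scope's findings; where none is used, only the missing prior plan remains.

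The size is unknown. Optional-scope use could be 0 to 30 patients, and the number of miscredited changes could be 0. A reader might be tempted to assume rates and quote one figure, for example 30 × 1/3 × 1/2 = 5 of 30 patients. The documents give neither rate, and that product also assumes that every such change is credited to Peregrine, so it should not be cited as the size of the bias.

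The conclusion assumes that steps 3 to 7 are carried out in the listed order and that the unseen questionnaire adds no entry before Peregrine. The primary visualization and safety endpoints are not affected. This is a worthwhile, inexpensive improvement to a secondary endpoint, not a flaw that undermines the study.

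**What to change.** In Section 6.2:
1. Right after step 3, have the physician record pathology seen and intended management (medication, CT, revision surgery).
2. Record the same items again right after step 4, before any optional scope.
3. If an optional scope is used, record any further change after step 5 as a separate entry.
4. Define the utility endpoint in Sections 4.3 and 7 as the paired change between entries 1 and 2, reported item by item with counts and percentages.
5. State in step 7 which scope the standard endoscope means, and reconcile this with the comparator named in the Synopsis and in Sections 6.1 and 7.
6. Add the entries to Table 1.

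The cost is a short CRF entry completed two or three times, brief pauses during an endoscopy under local or topical anesthesia, and a protocol amendment that goes through the approval described in Section 13. No procedure, visit or staff is added, and no clinical decision is prescribed. The entries must be made prospectively, because a plan held before Peregrine cannot be reconstructed later.

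The change removes reliance on recall and keeps the optional scopes out of the paired comparison. It does not remove expectation bias, since the same unblinded physician makes both entries, nor the effect of always using the 30° scope first. Both should be stated as limitations when the endpoint is reported.
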